Attention." Documented in the Statistical Design and Power attachment, the sample size is a compromise between feasibility and precision of estimates, and provides reasonable confidence interval widths for effect estimates. Inclusion criteria: a) be between the ages of 21 and 65, b) have consumed an average of at least five or more (four or more for females) standard alcoholic drinks per occasion once over the past year, c) have self-administered a quantity of alcohol that is equal to or greater than the dose that will be administered in the lab on at least three occasions in the past year, and d) be able to read and write in English fluently. Exclusion criteria: a) active psychosis, suicidal ideation/intent, or mania; currently receiving psychiatric treatment; have received psychiatric treatment in past year or currently experiencing significant psychiatric distress, b) in treatment or recovery from drug or alcohol use disorders or abstaining from alcohol, c) any suicide attempt history, d) pregnant/breast-feeding or immediate plans to become pregnant, e) any chronic health problems or medications that would preclude the use of alcohol, f) (to minimize adverse reactions to alcohol or inappropriate alcohol dose) < 6 feet tall and over 230 lbs., or > 6 feet tall and over 250 lbs. or weighing 15% below one's ideal body weight, g) (to minimize discomfort during lengthy study procedures) smoking more than 15 cigarettes a day, h) orange allergies, i) color-blind or sight-impaired, and j) knowing someone who has participated in this study. Given this is the first study to test the effects of AUA on suicide-related attentional bias, our exclusion criteria are conservative to reduce adverse events related to increased distress.

Procedures

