Manipulation Check and Dependent Variable Measurement: After the mood induction, participants will complete the PANAS-X subscales as a manipulation check (<2 min). Participants will then complete a Stroop⁴⁷ task modified to assess attention towards suicide-related cues (i.e., Suicide Stroop³). This modified Stroop task is a performance-based measure conducted via computer that documents response latencies on identification of the colors of words presented on the screen. Neutral (museum, paper, engine), negative (alone, rejected, stupid), positive (happy, success, pleasure), and suicide-related (suicide, dead, funeral) categories of words are presented, and greater response latencies indicate greater interference of the semantic content in naming the color. Participants will be instructed to indicate the word color as guickly and accurately as possible using red and blue keys. Stimuli will be presented using Empirisoft DirectRT software.⁴⁸ Trials will be presented in a random order to each participant. Interference for suicide-related words (i.e., suicide-related attentional bias) will be calculated by subtracting the response latencies for neutral words from the latencies for suicide-related words.³ Internal consistency coefficients for reaction time tasks like Stroop tasks are typically low⁴⁹⁻⁵⁰, and it has been suggested that using internal consistencies from past studies is inadvisable as sample characteristics can have a significant impact on the internal consistency.⁴⁹ Nonetheless, in our partial test, the internal consistencies for the interference scores (using a split-half coefficient) and the suicide trial reaction times were .49 and .86, respectively, which are typical of Stroop tasks⁵⁰⁻⁵¹ and much better than reliabilities in prior studies using the Suicide Stroop.²⁸ The Suicide Stroop has demonstrated construct validity through associations with past and future suicidal behavior.^{3,21} Thus. It serves as the primary outcome

of interest. Following the Stroop, participants will complete the 2-item Brief Hopelessness Measure³⁹ (a secondary outcome, see *Potential Problems* below).

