Pre-Manipulation Mood and Cognition (PANAS-X; Brief Hopelessness Measure)
Manipulation Procedures and Checks
Alcohol or placebo administration; Post drinking BrAC measurement; Manipulation check
Mood induction (positive or negative); Manipulation check: PANAS-X
Outcome Measure: Modified Stroop-Suicide (primary outcome of interest), Brief Hopelessness Measure
Post-Study Procedures: Detoxification (if applicable); Post-Study Verbal Interview, Paykel Suicide Scale
(current; risk screening for post study interview), Debriefing, Payment
Follow up Wollness Check Dhone Calle (day of day following, and wook following)

Follow-up Wellness Check Phone Calls (day of, day following, and week following)

Analytic plan

H1: We will quantify the number of individuals screened and the percentage who are eligible and participate. We will run descriptive statistics to quantify 1) prevalence of successful mood induction, 2) distress ratings post-study session, and 3) number of adverse events. Using measures of effect size, t-tests, and Chi square analyses, we will examine sociodemographic differences in these feasibility factors. H2: We will use measures of effect size, t-tests, and Chi Square analyses to examine sociodemographic differences in suicide-related attentional bias scores. H3: The interactive effect of mood and AUA on suicide-related attentional bias will estimated model be using а general linear of the form $\hat{Y} = \beta_0 + \beta_1 Alcohol + \beta_2 Mood + \beta_3 Alcohol \times Mood$. **H4:** The interactive effect of alcohol expectancies and AUA on suicide-related attentional bias will be estimated using a general linear model of the form $\hat{Y} = \beta_0 + \beta_1 Alcohol + \beta_2 Expectancies + \beta_3 Alcohol \times Expectancies$. For H3 and H4, we will use linear contrasts to estimate effects. Inferences will be conducted using 68% CIs for comparisons of interest, as significance testing is not a primary study aim. See Statistical Design and Power attachment.

Potential Problems, Alternative Strategies, Benchmarks for Success, and Impact

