Specific Aim 2, Hypothesis 2: Examine sociodemographic differences in suicide-related attentional bias. Suicide-related attentional bias will be higher among women, individuals with lower income, individuals ages 21-34, and individuals with heavier alcohol use than their comparators. Although racial differences are not observed in suicide attempts, we will explore racial differences in suicide-related attentional bias.

Analysis: Using measures of effect size and *t*-tests and Chi Square analyses where appropriate, we will examine potential these sociodemographic differences in suicide-related attentional bias scores.

Specific Aim 3, Hypothesis 3: Examine the conditional effect of AUA on suicide-related attentional bias by mood states. Individuals in the alcoholic beverage-negative mood condition will exhibit the greatest suicide-related attentional bias, followed by individuals in the placebo beverage-negative mood condition, placebo beverage-positive mood condition, and alcoholic beverage-positive mood condition.

Analysis: The interactive effect of mood and alcohol (Alcohol X Mood Induction) on attentional bias towards suicide-related cues (Stroop interference score, calculated by subtracting the response latencies for neutral words from the latencies for suicide-related words) will be estimated using a general linear model of the form $\hat{Y} = \beta_0 + \beta_1 Alcohol + \beta_2 Mood + \beta_3 Alcohol \times Mood$, where \hat{Y} is the average Stroop interference score, *Alcohol* is a binary indicator (1=yes, 0=no) of assignment to alcoholic beverage intake, and *Mood* is a binary indicator of assignment to the positive vs. negative mood induction (1 vs. 0). Among the positive mood induction group, the average effect of alcohol intake on Stroop interference scores is estimated by the sum of coefficients $\beta_1 + \beta_3$, while the average effect of alcohol intake in the negative mood induction group is estimated by the coefficient β_1 . Therefore, the coefficient β_3 estimates the differential effect of alcohol intake conditional on mood induction. We will use model-predicted means to estimate mean Stroop interference scores among the negative mood-alcohol condition participants. Measures of effect size (e.g. R², partial eta², Cohen's d) will be used to aid in interpretation. Inferences will be conducted using confidence intervals for the comparisons of interest, as statistical significance testing is not the primary goal of the study.

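### H2 compares Stroop scores between sociodemographic groups with no term for the randomised alcohol and mood conditions; the contrast stays valid, but adding the terms is a nearly free improvement (minor)

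*SAP*

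**What the plan says.** The SAP (Specific Aim 2, Hypothesis 2) predicts higher suicide-related attentional bias in women, in people with lower income, in "individuals ages 21-34, and individuals with heavier alcohol use than their comparators". The analysis is given in one sentence: "Using measures of effect size and *t*-tests and Chi Square analyses where appropriate", followed by "we will examine potential these sociodemographic differences in suicide-related attentional bias scores". The protocol (Analytic plan, H2) reads: "We will use measures of effect size, t-tests, and Chi Square analyses to examine sociodemographic differences in suicide-related attentional bias scores". Neither text names a condition term, a covariate or a restriction to one condition. That the four conditions are pooled is therefore read from the absence of any such term; the documents do not use the word.

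The outcome is measured after both manipulations. In the protocol (Manipulation Check and Dependent Variable Measurement) the post-induction mood scales come first, and then: "Participants will then complete a Stroop⁴⁷ task modified to assess attention towards suicide-related cues". No Stroop before the manipulations is listed in Table 1.

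The next hypothesis in the SAP, H3, orders the expected scores over the four alcohol-by-mood cells. H3 and H4 are analysed by general linear models that include Alcohol, and H4 keeps expectancies continuous. Enrolment requires participants to "be between the ages of 21 and 65", so H2 divides a 45-year span into one band and the rest. No cut is given for income or alcohol use.

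**The concern.** H2 analyses a score that the plan itself expects the randomised conditions to move, and it does so with a method that cannot use that knowledge. Differences between cells then count as unexplained variation in every H2 comparison, although condition is known for each participant. The SAP justifies its sample size by precision of estimates, and H2 is one of four stated aims.

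Two further matters bear on the same analysis. Participants who become aware of the aims or do not respond to the mood induction are removed from the initial analyses after randomisation, so balance of conditions across sociodemographic groups is not guaranteed in the analysed set. And if bias changes gradually with age, a two-group split at 34 uses only part of the information in recorded age.

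**Working it through.** **The plan's own figures.** The documents give no precision or power figure for H2. The SAP's figures for H3 (n=30 per cell, SD 1) reproduce, with .9945 as the 68% normal quantile:
- Half-widths: .9945 x sqrt(2/30) = .257 and .9945 x 2/sqrt(30) = .363 (stated .26 and .36).
- Detectable effects at two-sided .05 and 80% power: 2.80 x .258 = .72 and 2.80 x .365 = 1.02 (stated .72 and 1).

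The interaction of 1 is thus what the design could detect. The SAP does not say that it expects an effect of that size.

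**Inputs for H2.** N=120 is the SAP's 30 per cell. N=112 is what 150 x .75 = 112.5 leaves. The within-cell SD is 1. The mood effect of .32 is the protocol's partial-test value (Preliminary Data). The cell means below are assumptions, listed as alcohol-negative, placebo-negative, placebo-positive, alcohol-positive.

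**Step 1: SE without condition terms.** With between-cell variance v (the mean of the squared cell means), the SE is multiplied by sqrt(1+v).

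**Step 2: price of adjusting.** Three condition contrasts absorb on average 3/(N-1) of the variation in the group indicator. The adjusted SE is therefore multiplied by 1/sqrt(1-3/(N-1)), which is 1/sqrt(1-3/119) = 1.013 at N=120 and 1/sqrt(1-3/111) = 1.014 at N=112.

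**Step 3: net ratio, unadjusted to adjusted, at N=120.**

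| Scenario | Cell means | v | sqrt(1+v) | Net ratio |
|---|---|---|---|---|
| Mood effect .32 only | .16, .16, -.16, -.16 | .0256 | 1.013 | 1.013/1.013 = 1.00 |
| Interaction .5 | .41, .16, -.16, -.41 | .097 | 1.047 | 1.047/1.013 = 1.03 |
| Interaction 1, placebo cells equal | .5, 0, 0, -.5 | .125 | 1.061 | 1.061/1.013 = 1.05 |
| Interaction 1, strict H3 order | .66, .16, -.16, -.66 | .231 | 1.109 | 1.109/1.013 = 1.10 |

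At N=112 the ratios are the same to within .002. Simulation with equal groups agrees: no gain at d=.32, about 3% at an interaction of .5, and about 4-10% at an interaction of 1.

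**Step 4: validity.** In 8,000 simulated trials per scenario (N=120, random assignment), the unadjusted difference averaged -.001 and .002 when the truth was 0, and .500 and .499 when it was .5. Type I error was .050 to .052.

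**Step 5: chance imbalance is the same noise.** For two groups of 60, the share in negative mood differs by chance with SD sqrt(.25 x (1/60+1/60)) = .091. That shifts the comparison by .091 x .32 = .029 SD. The noise from v is sqrt(.0256) x sqrt(1/60+1/60) = .16 x .183 = .029. These are one quantity, already inside the t-test's SE, and must not be added.

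**Step 6: imbalance from exclusions.** If the analysed groups differed systematically by 10 percentage points in mood condition (an assumption), the shift would be .10 x .32 = .03 SD. In the last scenario the mood gap is .82, and the shift would be .10 x .82 = .08 SD.

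**Step 7: age.** For a linear trend and uniform ages, the squared correlation of age with an indicator holding share p is 3p(1-p). Whole years 21-34 are 14 of the 45 from 21 to 65, so p = .311 and 3 x .311 x .689 = .64. Other assumed age distributions gave 58-70%. For an assumed correlation of .25 at N=120, power is 79% with continuous age and about 59% with the split under uniform ages.

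**The case against.** The strongest reply is that nothing here is invalid. Conditions are randomly assigned, so condition is independent of sociodemographic group in expectation. The t-test estimates a legitimate difference averaged over conditions, with a correct SE. At the only empirical effect in the documents, adjustment gains nothing. The study is a pilot that explores effect sizes with 68% intervals, and no precision claim is made for H2. All of this stands, and it limits the point to a minor one.

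Four stronger readings are tempting, and the documents do not support them.
- A reader might infer that group differences are confounded with condition. Random assignment rules that out. The imbalance can become systematic only through exclusions, and then only if the pattern of exclusion across conditions differs between sociodemographic groups. Objective 1b will examine sociodemographic differences in induction success but does not predict any, and the removals apply to the initial analyses.
- A reader might treat the SAP's value of 1 as a mood main effect and compute a chance shift of about .10 SD. It is a detectable interaction, quoted for completeness.
- A reader might call the age split simply wrong. The hypothesis is itself about "individuals ages 21-34", and the t-test answers it directly. If bias changes in a step at 34, linear age is the less efficient choice.
- A reader might object to chi-square for a continuous score. The SAP limits its tests to where they are appropriate, so nothing needs correcting there.

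What remains is that the phrase about appropriateness adds no condition term, and that the known design factors are left out although including them needs no new data.

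**Conclusion.** The point holds as a minor improvement. H2 as written omits the randomised conditions from the analysis of a score that H3 expects them to shift. The estimate is unbiased and its SE valid under random assignment. After the 3 degrees of freedom are paid for, the avoidable loss is nil at d=.32, about 3% of the SE at an assumed interaction of .5, and about 4-10% at an assumed interaction of 1. Protection against imbalance from exclusions is a further benefit whose size the documents cannot settle.

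The age split could cost more, about 36% of the information. That figure needs both a linear trend and uniform ages, neither of which is in the documents. It supports a continuous analysis beside the stated contrast and gives no ground for replacing it.

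**What to change.** In the SAP, under Specific Aim 2, state that each H2 difference will be estimated from a linear model of the Stroop interference score on the sociodemographic factor plus Alcohol, Mood and Alcohol x Mood, with the same confidence intervals as elsewhere. Align the protocol's H2 sentence.

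Keep the 21-34 versus older contrast as the test of the hypothesis as worded. Report beside it a model with age continuous, and do the same for alcohol use and income where they are recorded as scores.

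The cost is SAP wording and 3 degrees of freedom per model, with data already planned for collection.

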Upon completion of this initial screening battery, participants will then complete a separate computer assessment battery, including measures of demographics and suicide and alcohol-related constructs (however, these will be kept to a minimum to mask study aims). Relevant to the current study aims, a measure of alcohol expectancies (Comprehensive Alcohol Expectancy Questionnaire [CAEQ]³⁴⁻³⁵) will be included. The CAEQ is a reliable and valid measure of alcohol expectancies, with confirmatory analysis supporting it in alcohol-dependent and college student samples.³⁶ The following CAEQ subscales will be used for the purposes of this investigation: Social Assertiveness/Positive Affect and Tension Reduction. We will also include items we developed regarding suicide-related alcohol expectancies (SRAEs), as there is no validated measure of suicide-related expectancies. These items will be dispersed throughout the CAEQ to keep subjects naïve to study aims. Our preliminary work supported the reliability and validity of the SRAE measure in a sample of 80 college students. The measure had high internal consistency (α =.96). Scores were normally distributed (Range=93; M=53.83, SD=23.70; Skewness=-0.11, Kurtosis=-0.91). Concurrent validity was supported. Hazardous drinkers reported greater SRAEs than non-hazardous drinkers (M=61.00, SD=16.39 vs. M=49.55, SD=26.27, d=0.52), and SRAEs were positively correlated with past year suicidal ideation (r=.43, p<.01). Finally, a measure of attentional abilities (Conners' Adult ADHD Rating Scales, Self Report: Long Version; [CAARS-LV]³⁷) will be included to reinforce the deception that the study is investigating broad attention. Participants will be compensated via cash gift card (\$20 for this session).

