Prior to analysis, Suicide Stroop scores will be evaluated for outliers. We will exclude: trials with incorrect responses, trials with response latencies ± 2 SD from each participant's mean response latency, participants with a mean response latency ± 2 SD from the overall sample's mean, participants whose error rate was +2 SD above the error rate for all participants. We will also examine the reliability, factor structure, and concurrent validity for the suicide-related alcohol expectancies measure (created for this study) prior to its use for Hypothesis 3. We will use exploratory factor analysis (with parallel analysis), Cronbach's alpha, and examine associations with AUDIT total scores and past suicidal ideation severity. Finally, we will confirm there were no pre-existing relevant differences in mood states between our mood and alcohol conditions by estimating measures of association (i.e., R²) between condition assignment and pre-manipulation sad, guilty, and joviality mood states.

Pre-Pilot tests: To finalize study procedures, for the 10 pre-pilot subjects, we will examine prevalence of mood induction effectiveness. If >50% fail the mood induction, we will replace it with another effective mood induction (imaginative film). We will also run frequencies to examine percentage of participants who are successfully deceived, expecting these percentages to be high (>90%). We will use these results to adjust the protocol in order to improve success of our mood manipulation and deception.

Specific Aim 1, Hypothesis 1a: To test the feasibility our experiment, we will first quantify the number of individuals who contact our lab about the study and the percentage who are eligible and participate. We will run descriptive statistics to quantify 1) prevalence of successful mood induction (expecting at least 75%), 2) distress ratings after the study session (expecting average ratings to be low), and 3) number of adverse events (expecting less than 1% of pilot subjects). **Objective 1b:** Using measures of effect size (i.e., Cohen's d, Cramer's V) and t-tests and Chi square analyses, we will examine sociodemographic differences (gender, age, race/ethnicity, income, and alcohol use history) in these feasibility factors.

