Specific Aim 4, Hypothesis 4: Explore the conditional effect of AUA on suicide-related attentional bias by alcohol expectancies. The relation of suicide-related alcohol expectancies with suicide-related attentional bias will be stronger among those in the AUA condition compared to those in the placebo condition.

Analysis: The interactive effect of expectancies and alcohol (Alcohol X Expectancies) on attentional bias towards suicide-related cues (Stroop interference score, calculated by subtracting the response latencies for neutral words from the latencies for suicide-related words) will be estimated using a general linear model of the form $\hat{Y} = \beta_0 + \beta_1 Alcohol + \beta_2 Expectancies + \beta_3 Alcohol \times Expectancies$, where \hat{Y} is the average Stroop

interference score, *Alcohol* is a binary indicator (1=yes, 0=no) of assignment to alcoholic beverage intake, and *Expectancies* is a continuous score of alcohol expectancies (higher scores indicate higher expectancies). The coefficient β_2 estimates the differential effect of expectancies conditional on alcohol intake. With the model, we

will estimate Stroop inference scores by alcohol conditions at the mean expectancy and ± 1 SD away from the mean, expecting that in the alcohol condition, expectancies will have a stronger association with attentional bias towards suicide scores. Measures of effect size (e.g. R², partial eta², Cohen's r) will be used to aid in interpretation. Inferences will be conducted using confidence intervals for the comparisons of interest.

Power and Sample Size Considerations

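### H4's Alcohol × Expectancies coefficient is sound as effect modification, but cannot be credited to expectancies themselves without a joint sensitivity model for drinking history and past ideation

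*SAP*

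**What the plan says.** SAP, Specific Aim 4, Hypothesis 4, is labelled exploratory and predicts that "The relation of suicide-related alcohol expectancies with suicide-related attentional bias will be stronger among those in the AUA condition". The model has an intercept, a binary Alcohol term, a continuous Expectancies score and their product. It has no term for drinking history or past ideation. The SAP will also report model-based Stroop scores by arm at the mean expectancy and one SD either side. It names β2 as the coefficient for the differential effect, although in the model as written β2 is the placebo-arm slope and β3 is the difference between arms.

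The protocol (Procedures, Screening and Session 1) describes the suicide-related alcohol expectancies (SRAE) items "in a sample of 80 college students". There, "Hazardous drinkers reported greater SRAEs than non-hazardous drinkers" (d=0.52), and "SRAEs were positively correlated with past year suicidal ideation (r=.43, p<.01".

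Table 1 of the protocol lists the AUDIT and the lifetime Paykel scale at Session 1. For the expectancy measure, the SAP (Statistical Design) uses this information only for a validity check: it will "examine associations with AUDIT total scores and past suicidal ideation severity". Separately, Hypothesis 2 expects higher bias scores in "individuals with heavier alcohol use than their comparators".

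**The concern.** Only one of the two variables in the H4 product is randomised. People with high suicide-related expectancies probably differ from the rest in how they drink and in whether they have had suicidal thoughts. If heavier drinkers, or people with past ideation, respond differently to the lab dose, the expectancy score stands in for that difference and β3 moves away from zero even when expectancies do nothing.

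What is at stake is interpretation. The protocol treats expectancies as a possible mechanism. Its Impact paragraph says later studies could test whether making them less salient reduces the bias. A β3 that really reflected drinking history or ideation would point that work at the wrong variable. Both candidate variables are already measured, so the plan can look at this at little cost, but at present it does not.

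**Working it through.** **1. The plan's own precision figures.** The SAP gives no figure for H4. For H3 at n=30 per cell and σ=1, with z(.84)=.994:
- simple effect: .994 × √(2/30) = .26
- interaction: .994 × 2/√30 = .36

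Both agree with the SAP.

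**2. The same calculation for β3 in H4.** With two equal arms, unit residual SD and expectancies in SD units, each arm's slope has variance 1/(N/2). The difference in slopes therefore has SE = 2/√N.
- N=120 (the SAP's 30 per condition): SE .183, 68% half-width .18
- N=112 (150 less 25%): SE .189, 68% half-width .19

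I use N=112. Stroop outlier exclusions would widen it further.

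**3. Correlations with expectancies.**
- Past-year ideation: r=.43, as reported.
- Hazardous drinking: the overall mean of 53.83 and the group means of 61.00 and 49.55 imply a hazardous share of (53.83−49.55)/(61.00−49.55) = .374, about 30 of 80. Then r = .52/√(.52² + 1/(.375×.625)) = .24. This is for hazardous status; the correlation with a continuous AUDIT total may differ.

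**4. What biases β3.** Let the omitted variable change the alcohol effect by γ SD per SD, and let the true expectancy interaction be zero. The planned model then gives an expected β3 of γ × r. The documents give no γ, so it is assumed. The last two columns are the chance that the 68% CI lies wholly above zero, 1 − Φ(.994 − γr/.189), which is 16% when γ=0.

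| γ (assumed) | γr at r=.24 | γr at r=.43 | CI above 0, r=.24 | CI above 0, r=.43 |
|---|---|---|---|---|
| .1 | .02 | .04 | 19% | 22% |
| .2 | .05 | .09 | 23% | 30% |
| .3 | .07 | .13 | 27% | 38% |
| .4 | .10 | .17 | 32% | 47% |

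Simulation at N=112 agrees closely.

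**5. What does not bias β3.** If the omitted variables have main effects only (assumed .3 each), simulated β3 averages about 0. The placebo slope β2, read as an effect of expectancies, is off by .3×.24 + .3×.43 = .20. The contrast between predicted placebo scores at +1 and −1 SD is off by twice that.

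**6. Which adjustment works.** With γ=.3 for both variables, β3 averages about .20 in the planned model.
- Adding AUDIT and ideation as main effects only: still about .20.
- Adding AUDIT with its product alone, at an assumed AUDIT–ideation correlation of .2: .3 × (.43 − .244×.2)/(1 − .244²) = .12 remains.
- Adding ideation with its product alone: .3 × (.244 − .43×.2)/(1 − .43²) = .06 remains.
- Adding both variables and both products together: about 0.

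**7. Price of the joint model.** For AUDIT–ideation correlations of .5 to 0, the variance inflation is 1.23 to 1.33. The SE rises by √1.23 − 1 = 11% to √1.33 − 1 = 15%, and the half-width goes from .19 to about .21 to .22.

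**The case against.** The strongest reply is that H4 answers the question it asks. It is exploratory and speaks of a relation that differs between arms. With alcohol randomised, β3 estimates exactly that. This stands, and it is why the planned model should stay.

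A second reply is that nothing in the documents shows the mechanism. The validation data show only that drinking and ideation correlate with expectancies. A reader might take Hypothesis 2 as evidence that the H4 interaction is confounded. It is not, because it predicts a main effect of heavier drinking, and main effects leave β3 unbiased. The nearest support is the protocol's belief that effects would be larger in suicidal people, which is an expectation and not an estimate.

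Third, the correlations come from college students. Here everyone must have drunk at or above the lab dose, and people with current ideation, any attempt or recent psychiatric treatment are excluded. Both correlations may be weaker. The planned validity check will show them in this sample. This also stands and limits the size, but that check does not estimate whether either variable modifies the alcohol effect.

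Fourth, adjustment is not clearly right. The protocol holds that expectancies may drive suicidal thoughts, so past ideation may follow from them. The .43 also concerns past-year ideation, whereas Table 1 lists the lifetime scale. Both points favour a sensitivity analysis over a replacement model.

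A reader might finally infer that the protocol means to act clinically on H4. It says only that future studies could test changing expectancies, with targeting as a downstream implication.

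**Conclusion.** The point holds in a limited form. β3 is a valid estimate of how the expectancy slope differs between alcohol and placebo. It is not evidence about expectancies as such if drinking history or past ideation also modifies the alcohol effect. The planned analysis offers no way to see how far that matters.

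Under an assumed modification of .1 to .4 and the protocol's correlations of .24 and .43, the misattributed part runs from .02, which is negligible, to .17, which is close to the 68% half-width of .19. If both variables act, the parts add. The modification is assumed throughout, and the correlations may not carry over to this sample. The documents do not support saying that H4 is confounded, only that it could be. For an exploratory aim this is an inexpensive improvement and not a flaw that undermines the study.

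**What to change.** In the SAP, Specific Aim 4, Hypothesis 4:

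- Keep the planned model as the main H4 analysis.
- Add one sensitivity model with mean-centred AUDIT total, mean-centred lifetime Paykel ideation, Alcohol × AUDIT and Alcohol × Paykel, all together. Main effects alone, or one covariate at a time, do not remove the bias.
- Report the planned and adjusted β3 side by side with 68% CIs. Set no retention threshold. In simulations with no true expectancy interaction and a modification of .4, roughly half to nearly three quarters of the spurious positive estimates kept more than half their size after adjustment, because the two estimates share most of their sampling error.
- Describe the result as effect modification by expectancies that drinking history or ideation may partly explain, and note that past ideation may itself follow from expectancies. Describe β2 and the predicted scores at ±1 SD as unadjusted associations.
- While editing, name β3 as the differential effect.

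The cost is SAP wording, four degrees of freedom and a standard error about 11% to 15% larger in the sensitivity model only. No new data are needed.
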